## PROTOCOL

- Full Title:** The Cellular Pharmacology of F-TAF in dried blood spots
- Short Title:** TAF-DBS
- Clinical Phase:** I-II
- IND Sponsor:** Exempt
- Principal Investigator:** [name].
- Sample Size:** Approximately 36 who complete the study timeline. IRB approvals will be sought for 72 subjects to allow for screen failures and drop outs.
- Study population:** HIV-uninfected adult participants at low risk for HIV infection. All participants must have a creatinine clearance >60 ml/min (MDRD equation) and no contraindicated medical conditions or medications.
- Participating sites:** The University of Colorado Anschutz Medical Campus.
- Study Design:** Approximately 36 HIV negative subjects will be enrolled. Enrollment will target approximately half women and one third African-Americans or Latino. However, strict quotas will not be imposed. Enrollment will proceed without the need to meet specific race/gender targets. Participants will be randomized to one of 6 sequences consisting of two directly observed dosing regimens, 33%/67%, 33%/100%, 67%/33%, 67%/100%, 100%/33%, and 100%/67%, expressed as % of daily dosing. Each dose regimen will have a duration of approximately 12 weeks. DBS/blood will be collected every week and hair will be collected at 3 week intervals. There will be a 12 week washout period between dose regimens. Additional samples will be collected during this washout period to determine elimination kinetics in hair and DBS/blood.
- The 33% and 67% dosing regimens will skip doses spaced by days (i.e. 67% is two daily doses followed by skipping a day, repeated for 12 weeks; 33% dosing is a daily dose followed by two skipped days, repeated for 12 weeks).
- Study Duration:** For participants, the study lasts for approximately 36 weeks. Recruitment and enrollment will continue for approximately one year, the total study duration is approximately two years.
- Study Regimen:** Volunteers will receive 200mg and 25mg of emtricitabine and tenofovir alafenamide fumarate (F-TAF) according to the regimens outlined above. This medication will be donated by Gilead Sciences, and managed by the University of Colorado Hospital Investigational Pharmacy.

### Primary objectives:

- 1) Define the expected concentrations and dose-proportionality for TFV-DP in DBS using directly observed F-TAF therapy at 33%, 67%, and 100% of daily dosing.
- 2) Establish a model to predict adherence rate to F-TAF by level of TFV-DP in DBS.

## STATISTICAL CONSIDERATIONS

### Primary outcomes

**Primary outcome 1.** The study was powered on dose proportionality of TFV-DP in DBS. Means, variances and dose proportionality will utilize measured concentrations at steady-state ( $C_{ss}$  at 12 weeks). Measured values will be validated with fitted values from PK modeling approaches (eg NONMEM).(22) The sample size was based upon demonstrating dose proportionality. Under the power model,  $C_{ss}=a(\text{dosing})^b e$ , dose proportionality dictates the 90% CI for  $b$  is in (0.8, 1.25).(23) We assume an incomplete block design with each subject receiving 2 (of 3) doses, providing 6 permuted dose sequences (figure 2). An estimate of within subject CV was  $2 \cdot \max(CV) = 0.20$  based on 5 replicate TFV-DP DBS samples from 2 subjects. Assuming a significance level of 0.05, we estimate a sample size of  $n=36$  subjects (6 per dose sequence).(23) If dose proportionality is not shown, we will consider dose as a predictor of  $\log(C_{ss})$  as a linear ( $b \neq 1$ ) or a categorical effect interacted with time. Secondary outcomes such as the effects of race, gender and genetics, will be evaluated with models utilizing likelihood ratio tests and AIC to compare nested and non-nested models. (23-27)

**Primary outcome 2.** The goal is to determine DBS TFV-DP cut points associated with adherence levels. For the primary analyses, we will attempt to discriminate 33%, 67% and 100% dosing based upon TFV-DP in DBS. Power calculations conservatively assume a single measured  $C_{ss}$  observation at week 12, dose as a categorical predictor and 1 dose regimen per subject. Sample sizes of  $n=16$  for each regimen achieve 90% power to detect a difference of 0.27 (0.30) between the area under the ROC curve (AUC) under the null hypothesis of 0.50 and an AUC under the alternative hypothesis of 0.77 (0.80) using a two-sided z-test at a significance level of 0.05. In practice, a proportional odds logistic approach which allows for an ordinal outcome (25, 26, 28) and extensions which control for correlations between repeated measurements on a subject will be utilized. (29) Finally, we will employ PK models from aim 1 to simulate TFV-DP for other dose regimens to estimate cut points for adherence rates other than 33%, 67% and 100%.

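### Do limits of 0.8 and 1.25 on the exponent b, which are unequal once turned into concentration ratios, need to be changed?

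*Combined protocol and SAP*

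**What the plan says.** The first primary objective is to define expected concentrations and "dose-proportionality for TFV-DP in DBS using directly observed F-TAF therapy at 33%, 67%, and 100% of daily dosing". Under Statistical Considerations, Primary outcome 1, week-12 concentration is modelled as a constant times dosing raised to the power b, with an error term, and "dose proportionality dictates the 90% CI for $b$ is in (0.8, 1.25". A reference is cited for this rule and again for the sample size. The same section states that "The sample size was based upon demonstrating dose proportionality", and gives 36 subjects, 6 per sequence, each receiving two of the three dosing levels. The planning within-subject CV of 0.20 is twice the largest CV seen and is "based on 5 replicate TFV-DP DBS samples from 2 subjects". If proportionality is not shown, dose enters the model for log concentration either linearly with b free or as a categorical effect interacted with time. No margin is given for the dose-normalised concentration ratio, and no power is stated for this outcome.

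**The concern.** The pair 0.8 and 1.25 is familiar as a margin for a ratio of means, where the two limits mirror each other about 1 on the log scale. Here the pair is placed on an exponent. Mirror-image departures of an exponent are 1 - d and 1 + d, so the stated interval is off centre: its midpoint is (0.8 + 1.25)/2 = 1.025. It looks as though a ratio margin was carried over without rescaling for the dosing range.

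This is the decision rule for the outcome on which the study was powered, and it also decides whether the fallback dose models are used. If the limits are lopsided, a true shortfall is sent to the fallback more often than an equal excess, and some excesses above 25% at full dosing would be compatible with a declaration of proportionality.

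**Working it through.** **Inputs.** Limits 0.8 and 1.25 on b, 90% CI, CV 0.20 and n = 36 are from Primary outcome 1. The dosing levels are from the Primary objectives ("directly observed F-TAF therapy at 33%, 67%, and 100% of daily dosing"). The range is r = 3, because under Study Design "33% dosing is a daily dose followed by two skipped days, repeated for 12 weeks". There are 12 subjects per pair of levels (Table 1). A period term, giving 34 df, is an assumption.

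**Limits as ratios.** Under the plan's model the dose-normalised ratio between two levels is r^(b-1).

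- 100% v 33%: 3^(-0.2) = 0.803 and 3^(0.25) = 1.316.
- At b = 1.25 the other pairs give 2^(0.25) = 1.189 and 1.5^(0.25) = 1.107.
- Going the other way, a 0.80-1.25 ratio over r = 3 corresponds to b from 1 + ln(0.80)/ln(3) = 0.797 to 1 + ln(1.25)/ln(3) = 1.203.

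**Precision.** Var(b) = 2 ln(1 + CV²) / [12 (ln²2 + ln²3 + ln²1.5)] = 0.0784/22.22 = 0.00353, so SE(b) = 0.0594. The 90% CI half-width is 0.1005.

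**The plan's sample size.** At b = 1 the stated rule passes 94.4% of the time with n = 36. The smallest multiple of 6 giving 90% is 36 (31 without that restriction). So n = 36 is consistent with a 90% target, although the plan does not name one for this outcome.

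**Pass probabilities, n = 36, CV 0.20.**

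| True b | 100% v 33% ratio | Stated limits (0.8, 1.25) | Scaled limits (0.797, 1.203) |
|---|---|---|---|
| 0.90 | 0.90 | 50.2% | 52.2% |
| 0.95 | 0.95 | 79.6% | 80.5% |
| 1.00 | 1.00 | 94.4% | 91.2% |
| 1.05 | 1.06 | 94.4% | 80.5% |
| 1.10 | 1.12 | 79.6% | 52.2% |
| 1.203 | 1.25 | 19.2% | 5.0% |
| 1.25 | 1.32 | 5.0% | 0.8% |

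Under the stated rule the pass rate is also 5.0% at b = 0.8, and it is 4.5% at b = 0.797 (ratio 0.80). Simulation of the 36-subject design agrees with the stated-limit figures to within 0.003.

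**What can actually pass.** The whole interval must lie inside the limits. At SE 0.0594 the largest passing estimate is 1.25 - 0.1005 = 1.1495, a ratio of 3^(0.1495) = 1.18. At CV 0.10 the half-width is 0.0506, the largest passing estimate is 1.1994, and the ratio is 1.245.

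**Cost of scaling.** At b = 1 the pass rate falls from 94% to 91% at CV 0.20, from 80% to 71% at CV 0.25, and from 59% to 46% at CV 0.30. For 90% power at CV 0.20, the n required (multiples of 6) goes from 36 to 48 at b = 1.05 and from 54 to 108 at b = 1.10. At b = 1 it stays at 36. CVs of 0.25 and 0.30 are assumptions; 0.10 is half the planning value.

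**The case for a change.** The strongest case for changing the plan is that unequal treatment does not depend on any assumed margin. Ratios of 0.90 and 1.12 are mirror images, yet they pass 50% and 80% of the time, and b = 1.05 passes exactly as often as true proportionality. With a better assay than planned the contrast sharpens: at CV 0.10, true ratios of 0.80 and 1.25 pass 4.0% and 45.6% of the time. At CV 0.30 they pass 4.6% and 12.8%. The planning CV rests on very few subjects, so the favourable case is possible. One sentence giving the ratio meaning of the limits would cost no power.

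The arithmetic stands, but it does not show an error. The values 0.90, 1.10 and 1.203 all lie inside the stated limits, so passing there is power, not a false claim. The 19% at a ratio of 1.25 becomes a false-pass rate only if a 0.80-1.25 ratio margin is assumed, and the documents set none. The contrast of 32% up with 20% down also overstates the gap, because a 0.80-1.25 ratio range is itself 25% up and 20% down. The excess width is 1.32 against 1.25, on one side and for one of three dose pairs. A sentence translating the limits into ratios would be helpful in a report, but it alters no result.

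**Conclusion.** The point is correct as a description and calls for no change. The rule names the model, the parameter, the interval and the limits, so an analyst can apply it without judgement. Its false-pass rate is 5% at each limit. The lower limit already matches a 0.80 ratio (0.8 v 0.797 on b). The upper one is looser than a 1.25 ratio (1.25 v 1.203), but at the planned precision no estimate more than about 18% above proportional would pass.

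Scaled limits would rest on an assumed margin. They would gain symmetry almost entirely by failing more excesses: 80% to 52% at b = 1.10, against 50% to 52% at b = 0.90. That is a fair trade-off for the sponsor to settle either way. Little hangs on the label, since a fallback model is planned and the 33%, 67% and 100% cut points of Primary outcome 2 come from observed levels.

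The figures assume a within-subject analysis with a period term, log-normal error and 36 completers. The cited source for the rule could not be seen and may explain the limits.

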### Enrollment/Stratification/Randomization/Blinding Procedures

This is a randomized open label observational study. Each subject will be randomized to one of 6 possible dosing regimens shown in the table below (Table 1). For each study period, block randomization will be used to ensure that Dosing Groups are balanced across enrollment time. The randomization will be programmed using R software (<http://cran.r-project.org/> , The R Foundation for Statistical Computing).

Table 1: All possible randomization scenarios

Dosing group	1	2	3	4	5	6
Period 1	33	33	67	67	100	100
Period 2	67	100	33	100	33	67
N (36 total)	6	6	6	6	6	6

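### Does the power model for primary outcome 1 need a written subject and period term before its 90% CI can be trusted?

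*Combined protocol and SAP*

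**What the plan says.** The combined protocol and SAP, Statistical Considerations, Primary outcomes, gives one equation for primary outcome 1, "C_{ss}=a(\text{dosing})^b e". Proportionality is shown if the 90% CI for b lies in (0.8, 1.25). The data are the measured steady-state concentrations at week 12, and fitted values from PK modelling (NONMEM is the example) serve as validation.

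The design and sizing come next: "We assume an incomplete block design with each subject receiving 2 (of 3) doses, providing 6 permuted dose sequences (figure 2"). The variability used for sizing is a within-subject CV of 0.20, twice the largest CV seen, "based on 5 replicate TFV-DP DBS samples from 2 subjects". Then "Assuming a significance level of 0.05, we estimate a sample size of" 36, six per sequence. No target power or true value of b is given.

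Under primary outcome 2, the ordinal logistic approach is to be used and "extensions which control for correlations between repeated measurements on a subject will be utilized". No such sentence appears under outcome 1.

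Period appears only in the design. The randomisation section says "For each study period, block randomization will be used to ensure that Dosing Groups are balanced across enrollment time", and the Study Design entry says "There will be a 12 week washout period between dose regimens".

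**The concern.** The CI for b decides the outcome on which the study was powered. Each subject contributes two values, which will be correlated if people differ in their usual TFV-DP level. An equation with one error term, read as a fitting instruction, treats 72 values as independent and puts between-subject variation into the error. That outcome 2 mentions correlation and outcome 1 does not makes the omission look real. The stake would be a truly proportional drug failing the rule because its CI was needlessly wide. A shift in concentrations between the two periods would likewise go into the error if period were left out.

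**Working it through.** **Inputs.** From the plan: margins 0.8 and 1.25, a 90% CI, within-subject CV 0.20, and six subjects in each of the six Table 1 sequences. Doses are coded 1/3, 2/3 and 1. Assumed, because the plan gives no figure: the between-subject CV, any period shift, and the true b.

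**1. Is n=36 consistent with a within-subject analysis?** The figure cannot be strictly reproduced without a target power and a true b, but it can be checked.

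- Log-scale SD: √ln(1 + 0.20²) = 0.198.
- The log-dose differences within a subject are ln 2 = 0.693, ln 3 = 1.099 and ln 1.5 = 0.405. Each pair of doses is taken by 12 subjects, so the within-subject sum of squares of log dose is 12 × (0.693² + 1.099² + 0.405²)/2 = 11.11.
- SE(b) = 0.198/√11.11 = 0.0594. With subject and period fitted there are 34 df and t = 1.691, so the half-width is about 1.691 × 0.0594 = 0.100.
- Power at b = 1, normal approximation: Φ(0.20/0.0594 − 1.691) + Φ(0.25/0.0594 − 1.691) − 1 = Φ(1.68) + Φ(2.52) − 1 ≈ 0.947. Allowing for the estimated variance gives 94.4%.
- At b = 0.95 the lower margin governs: Φ(0.15/0.0594 − 1.691) = Φ(0.83) ≈ 0.797; allowing for the estimated variance, 79.6%.

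So 36 subjects give about 80% power at b = 0.95 or 94% at b = 1 when subject effects are removed. A pooled fit could not have been sized from the plan's inputs, since it also needs a between-subject CV and none is stated.

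**2. What would a literal pooled fit do?** The total sum of squares of log dose is 14.81, so the between-subject part is 14.81 − 11.11 = 3.70. With two values per subject, the squared subject totals of centred log dose sum to 2 × 3.70 = 7.41, and 7.41/14.81 = 0.50. Hence

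- true variance of b: (σ_w² + 0.50 σ_b²)/14.81
- variance the pooled fit reports, approximately: (σ_w² + σ_b²)/14.81

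The reported variance exceeds the true one whenever subjects differ at all, so the error is always towards caution. At a between-subject CV of 0.3, σ_w² = 0.0392 and σ_b² = ln 1.09 = 0.0862. The true SE is √(0.0823/14.81) = 0.0745, and the reported SE is about √(0.1254/14.81) = 0.092.

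Simulation of the Table 1 layout (20,000 trials per row, b = 1, within-subject CV 0.20):

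| Assumed between-subject CV | Pooled: power | Pooled: 90% CI coverage | Pooled: false claim at b = 1.25 / 0.80 | Subject effect: power |
|---|---|---|---|---|
| 0 | 98% | 90% | 5.1% / 4.9% | 94% |
| 0.2 | 87% | 94% | 3.0% / 2.8% | 94–95% |
| 0.3 | 63% | 96% | 2.2% / 2.2% | 94% |
| 0.4 | 33% | 96% | 1.6% / 1.6% | 94% |
| 0.5 | 10% | 97% | 0.7% / 0.7% | 94% |

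The loss is real for that reading, but its size depends wholly on a CV the documents do not give. Up to about 0.14 the pooled fit has no less power than fixed subject plus period.

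**3. Does the choice of fixed or random subjects matter?** Little. In a separate 40,000-trial simulation with doses coded 0.33 and 0.67, at a between-subject CV of 0.3, the half-width is 0.099 with fixed subjects and 0.096 with random subjects by REML. Coverage is 90% for both, and power is 95% and 96%.

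**4. Does period matter?** Table 1 puts each dose in each period for 12 subjects, and the signed log-dose differences sum to zero over the six sequences. Omitting period therefore leaves b unbiased among completers, and including it leaves SE(b) at 0.0594. With a subject effect but no period term, assumed shifts of 0, 10%, 20% and 30% give power of 94%, 93%, 89% and 81%.

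**The case for a change.** The strongest case for a change is that a decision rule should not depend on the analyst's inference. The equation is the only formula given for the primary test, and the fallback modelling of dose names neither subject nor period. The PK modelling only validates measured values and does not supply the CI for b. Two analysts could report different intervals, and one added sentence would prevent that at no cost to n.

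What stands is that the block term is not written out and the choice of fixed or random is left open. That choice moves the half-width by 0.003 (0.099 against 0.096).

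What does not stand is that the pooled fit is an equally natural reading. The equation sits in the sentence that defines proportionality, where it gives the mean structure. The sentences after it name a block design and a within-subject CV, and analysing a block design ordinarily means fitting blocks. The rule and n=36 also cite a reference that is not available here, so neither side can rest on its contents.

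On period, the plan suggests no shift between periods, and a 12-week washout separates them. A 10% shift would cost about one percentage point of power; the larger losses need shifts of 20% or more.

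**Conclusion.** No change to the plan follows. The missing subject term is abbreviated notation: the stated design and the CV used for sizing already point to a within-subject analysis. That analysis gives a 90% CI with 90% coverage and about 94% power at b = 1. The low power figures belong to a reading the plan does not adopt, under between-subject CVs it does not state. Even on that reading, false claims of proportionality become rarer. A period term would be harmless and is optional.

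The 94% is conditional on b = 1 and a within-subject CV of 0.20. It falls to 79.6% at b = 0.95, and to 59% at b = 1 if that CV is 0.30. Those sensitivities concern the planning values and do not depend on whether the subject term is written down.

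### Likelihood ratio tests of race, gender and genetics on 36 subjects carry no small-sample correction; with the usual chi-square reference their size would be about 6-9% at a nominal 5%

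*Combined protocol and SAP*

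**What the plan says.** Under Primary outcomes (Primary outcome 1), the plan lists "Secondary outcomes such as the effects of race, gender and genetics" and says they will be evaluated with "models utilizing likelihood ratio tests and AIC to compare nested and non-nested models". It does not give the reference distribution for the likelihood ratio statistic, a choice between ML and REML, the coding of race or genotype, whether the factors enter one model together, or a significance level for these tests.

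The only level in that paragraph belongs to the sample size for dose proportionality: "Assuming a significance level of 0.05, we estimate a sample size of" 36. The design is an "incomplete block design with each subject receiving 2 (of 3) doses", and the protocol synopsis gives the sample size as "Approximately 36 who complete the study timeline". At week 12 of each regimen this yields 36 × 2 = 72 Css values from 36 people. The synopsis targets about half women and one third African-American or Latino participants, without strict quotas.

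**The concern.** The chi-square reference for a likelihood ratio test is a large-sample approximation. For a factor that is constant within a subject, the relevant sample is the number of subjects. Maximum likelihood divides the residual sum of squares by n and not by n minus the number of mean parameters. The between-subject variance is therefore estimated too low and the test statistic comes out too large. With 36 subjects the effect is visible, and it grows with each adjusting term.

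What is at stake is the calibration of the p-values for the secondary covariate effects: they would be somewhat smaller than they should be.

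**Working it through.** **1. The plan's own figure.** The plan has no error rate for the covariate tests. Its figure is n = 36, based on the criterion that "dose proportionality dictates the 90% CI for $b$ is in (0.8, 1.25"). Inputs from the same paragraph: within-subject CV 0.20, two of three doses per subject, six sequences of six.

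- Log-scale SD = sqrt(ln(1 + 0.20²)) = 0.198.
- Each pair of doses is taken by 12 subjects, so the sum of squared log-dose differences is 12 × (ln 2² + ln 3² + ln 1.5²) = 12 × (0.480 + 1.207 + 0.164) = 22.2.
- SE of b = sqrt(2 × 0.198² / 22.2) = 0.059.
- The probability that the 90% interval lies inside the limits is 94% at b = 1 with 36 subjects, and 89% with 30.

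The plan states no power. If 90% at b = 1 is assumed, 36 is the smallest multiple of six that reaches it, so the figure is reproduced.

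**2. Exact size of the uncorrected test.** For a subject-level factor analysed on subject means, with n subjects, p mean parameters in the larger model and q degrees of freedom for the tested factor:

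- LRT = n ln(RSS0/RSS1), which is rejected when it exceeds c, the 95% point of chi-square on q df.
- This is the same as F > [(n − p)/q] × [exp(c/n) − 1].
- True size = P(F(q, n − p) exceeds that cutoff).

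With n = 36, exp(3.841/36) − 1 = 0.1126 for q = 1, and exp(5.991/36) − 1 = 0.1811 for q = 2.

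| Test (assumed model) | q | p | Cutoff implied by chi-square | Correct F cutoff | True size |
|---|---|---|---|---|---|
| Gender alone | 1 | 2 | 34 × 0.1126 = 3.83 | 4.13 | 5.9% |
| Three race groups alone | 2 | 3 | (33/2) × 0.1811 = 2.99 | 3.28 | 6.4% |
| Gender or binary race, with two genotype groups | 1 | 4 | 32 × 0.1126 = 3.60 | 4.15 | 6.7% |
| Gender or binary race, with three genotypes | 1 | 5 | 31 × 0.1126 = 3.49 | 4.16 | 7.1% |
| Three genotypes, with gender and binary race | 2 | 5 | (31/2) × 0.1811 = 2.81 | 3.30 | 7.6% |
| Race or genotype (three groups each), with gender | 2 | 6 | (30/2) × 0.1811 = 2.72 | 3.32 | 8.2% |
| The same, plus a dose term | 2 | 7 | (29/2) × 0.1811 = 2.63 | 3.33 | 9.0% |

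**3. Simulation of the mixed model.** Random-intercept ML fits were run with 36 subjects and two doses each. The main runs used within-subject SD 0.20 and assumed between-subject SD 0.1 to 0.4, with 4,000-6,000 null trials per setting (Monte Carlo error about 0.3-0.4 points). Across these and further runs with other assumed splits and variances, the size at nominal 5% was:

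- gender alone, 5.5-6.5%;
- race alone in three groups, 5.7-7.1%;
- gender adjusted for race and genotype, 6.9-7.3%;
- race adjusted for gender and genotype, 7.8-9.2%.

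**4. After the change.** In 40,000 null data sets of subject means, race on 2 df was adjusted for gender, genotype and mean dose. The chi-square likelihood ratio test rejected in 8.9% and the F test on (2, 29) df in 4.99% of the same data sets.

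**The case against.** The strongest reply is that these error rates belong to an assumed analysis. The plan names likelihood ratio tests but no chi-square reference, no level, no joint model and no rule for declaring an effect. The methods it cites cannot be seen here. A factor tested alone runs only about one to two points high, and the 9% figure needs three race groups, three genotypes and seven mean parameters. The one-third target for African-American or Latino participants can equally be read as a two-group contrast, which gives about 7%. The calculation also uses two values per subject, whereas blood spots are collected weekly and the plan mentions PK modelling.

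All of that stands, and it limits the size of the point. It does not remove it. A likelihood ratio test named without qualification is conventionally referred to chi-square, and that reference is too liberal in every configuration examined.

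A reader might also infer three stronger things that the documents do not support:

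- *Adherence cut points for separate groups become unsafe.* The plan bases its cut points on TFV-DP by dosing level and nowhere says that they will depend on race, gender or genetics.
- *AIC is faulty for the same reason.* The sentence is naturally read as likelihood ratio tests for nested models and AIC for non-nested ones. AIC is not a 5% test: even in large samples it admits a null 2-df term with probability exp(−2) = 13.5%. Replacing it is a matter of preference.
- *Covariate effects will be declared too readily.* The plan has no declaration rule for these secondary effects.

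**Conclusion.** The point holds as a conditional one. With 36 subjects, a chi-square reference and an assumed 5% level, the covariate tests have size of about 6-7% for one factor alone and about 7-9% when the factors are adjusted for each other. The excess is one to four percentage points. It would be wrong to say that the tests in general run at close to double their nominal level: only the largest assumed model comes near that.

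The figures rest on normal log(Css), a random intercept, and assumed covariate splits and between-subject SD. Nonlinear PK models of the weekly data were not examined. Neither primary outcome depends on these tests, so the interval for b and the discrimination of dosing levels are untouched. This is a cheap improvement.

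**What to change.** Amend the sentence on secondary outcomes under Primary outcome 1. For effects of race, gender and genetics on log(Css), replace the likelihood ratio tests with F tests from REML mixed models, using Kenward-Roger or Satterthwaite degrees of freedom. Where covariates are assessed in a nonlinear PK model, use a parametric-bootstrap likelihood ratio test. State the significance level and whether the factors are fitted together. Any AIC comparison of models that differ in fixed effects should stay on ML fits; no other change to AIC is asked for.

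The cost is one or two sentences and a software option, plus computing time if the bootstrap is used. No extra subjects, visits or samples are needed. The downside is slightly larger p-values for these secondary effects.

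### Can 16 per regimen give 90% power at both AUC 0.77 and AUC 0.80, as Primary outcome 2 states?

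*Combined protocol and SAP*

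**What the plan says.** In the combined protocol and SAP, Statistical Considerations, Primary outcome 2, the aim is to tell 33%, 67% and 100% dosing apart from TFV-DP in DBS. The power statement is that 16 subjects "for each regimen achieve 90% power to detect a difference of 0.27 (0.30) between the area under the ROC curve (AUC") under a null of 0.50 and "an AUC under the alternative hypothesis of 0.77 (0.80) using a two-sided z-test at a significance level of 0.05". The calculation is described as conservative: a single week-12 value, "dose as a categorical predictor and 1 dose regimen per subject".

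Three things are left unsaid: which regimens are compared with which, which variance formula was used for the AUC, and what the bracketed values denote.

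The same section says that in practice an ordinal (proportional odds) model will be fitted and that "extensions which control for correlations between repeated measurements on a subject will be utilized". Under Primary outcome 1 it says "We assume an incomplete block design with each subject receiving 2 (of 3) doses" and "The sample size was based upon demonstrating dose proportionality". The protocol synopsis gives the sample size as "Approximately 36 who complete the study timeline", and Table 1 in the randomisation section puts 6 subjects in each of 6 sequences.

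**The concern.** With the sample size, the test and the comparison fixed, power increases with the true AUC. A design with exactly 90% power at 0.77 must have more than 90% at 0.80. A reader who takes both values to refer to one pair of regimens, 16 against 16, and who puts the null standard error in the critical value, finds about 80% at 0.77. The chance of missing the first-listed effect would then be about 20% rather than 10%, in the only power statement given for a primary outcome.

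The head count adds to the doubt. Sixteen in each of three regimens at one regimen per subject is 3 × 16 = 48 subjects, and 36 are planned.

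**Working it through.** **Inputs.** From Primary outcome 2: 16 per regimen, null AUC 0.50, alternatives 0.77 and 0.80, two-sided z-test at 0.05 (critical value 1.960). From Table 1: 6 sequences of 6 subjects, two regimens each. The variance formula is not stated, so it is an assumption here; the steps use Hanley–McNeil, and ranges over other formulas follow.

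**Formulas.** For groups of m and n:

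- V(A) = [A(1−A) + (m−1)(Q1−A²) + (n−1)(Q2−A²)] / (mn), with Q1 = A/(2−A) and Q2 = 2A²/(1+A)
- Power = Φ{[(A−0.5) − 1.960·SE0] / SEA}, with SE0 = √V(0.5) and SEA = √V(A)

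At 0.50, Q1−A² = Q2−A² = 0.08333. At 0.77 they are 0.03312 and 0.07704. At 0.80 they are 0.02667 and 0.07111.

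**Step 1: one regimen against one other, 16 vs 16.**

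- SE0 = √[(0.25 + 30 × 0.08333)/256] = √0.010742 = 0.1036, so 1.960·SE0 = 0.2031
- AUC 0.77: SEA = √[(0.1771 + 15 × 0.03312 + 15 × 0.07704)/256] = 0.0845. Power = Φ[(0.27 − 0.2031)/0.0845] = Φ(0.791) = 78.5%
- AUC 0.80: SEA = √[(0.16 + 15 × 0.02667 + 15 × 0.07111)/256] = 0.0797. Power = Φ[(0.30 − 0.2031)/0.0797] = Φ(1.215) = 88.8%

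**Step 2: one regimen against the other two, 16 vs 32.**

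- SE0 = √[(0.25 + 46 × 0.08333)/512] = 0.0893, so 1.960·SE0 = 0.1750
- AUC 0.77: SEA = √[(0.1771 + 15 × 0.03312 + 31 × 0.07704)/512] = 0.0773. Power = Φ(1.228) = 89.0%
- AUC 0.80: SEA = √[(0.16 + 15 × 0.02667 + 31 × 0.07111)/512] = 0.0735. Power = Φ(1.701) = 95.6%

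**Step 3: range over variance formulas** (Hanley–McNeil, Obuchowski, parametric binormal, Mann–Whitney under equal-variance normals), null SE in the critical value.

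| Comparison | AUC 0.77 | AUC 0.80 |
|---|---|---|
| 16 vs 16 | 78.5–82.1% | **88.8–91.6%** |
| 16 vs 32 | **89.0–92.5%** | 95.4–97.7% |

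The stated 90% is reproduced on the diagonal: 0.77 for one against two, 0.80 for a pair. Neither row gives 90% in both columns.

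**Step 4: another convention.** If the alternative SE is used in both places, 16 vs 16 gives Φ(0.27/0.0845 − 1.960) = Φ(1.234) = 89.1% at 0.77 and Φ(0.30/0.0797 − 1.960) = Φ(1.804) = 96.4% at 0.80. Over the four formulas the ranges are 85.2–91.6% and 93.5–97.7%. With most of these formulas, the plan's 90% read as a floor holds to within about a point for one pairwise test.

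**Step 5: what the design supplies.** Each regimen occurs in 4 of the 6 sequences, so 4 × 6 = 24 observations per regimen. For 24 vs 24 at 0.77, treated as independent: SE0 = √[(0.25 + 46 × 0.08333)/576] = 0.0842; SEA = √[(0.1771 + 23 × 0.03312 + 23 × 0.07704)/576] = 0.0686; power = Φ[(0.27 − 0.1650)/0.0686] = Φ(1.530) = 93.7% (93.4–95.3% over the formulas). Simulating the six-sequence design with normal data and within-subject correlation from 0 to 0.9 gives about 93% or more at 0.77 and about 97% or more at 0.80, for either comparison. Positive correlation does not lower power here, because half of the subjects in any pair of regimens receive both (12 of 24).

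**The case for a change.** The best case for an edit has three parts.

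First, no single comparison under a single convention gives 90% at both values, and the plan does not describe two comparisons. That is correct, and the two-comparison reading is an inference from the numbers. But the single-comparison reading is equally an inference. The plan has three regimens to separate and gives a pair of values, and each value returns about 90% under a natural comparison. That is not evidence of a miscalculation.

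Second, 16 vs 32 at one regimen per subject needs 48 subjects. As a count this stands, and it makes the word conservative awkward: 36 subjects used once each would be 12 per regimen, where pairwise power is only about 64–68% at 0.77 and 76–80% at 0.80. But one regimen per subject is a simplification for the calculation. Each subject contributes two regimens, and the 24 observations per regimen exceed the 16 assumed.

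Third, the fix is only a sentence. Yet writing in about 80% (90%) would record an assumption about comparison and variance formula that the documents do not support. Only the authors of the calculation can supply the missing labels.

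**Conclusion.** The concern does not establish an error. What remains is a reporting gap: the comparison, the variance formula and the meaning of the brackets are not given. Read as a single pairwise test with the null SE, power at 0.77 would be about 80%, some 10 points below the stated figure. Read as two comparisons, both figures are right to within about 2.5 points.

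The choice between these readings affects nothing in the trial. The 36 subjects were fixed by the dose-proportionality calculation. The z-test on the AUC is not the planned analysis; the ordinal model with allowance for repeated measurements is, and analysts will fit it to both periods. On the data the design provides, power for a simple AUC test is at least about 93% at 0.77, above the stated 90%. This last figure assumes that all 36 subjects complete both periods, normally distributed values with equal variance, and within-subject correlation between 0 and 0.9. No change to the plan follows.
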